3.7.5.1.3 Fluid Balance

A fluid balance will be calculated by subtracting the “urine volume” from the “fluid intake.” Fluid balances will be calculated by the sponsor; therefore, entry in the eCRF will be unnecessary.

3.7.5.1.4 Serum Sodium Concentration, Serum Potassium Concentration, Serum Osmolality, and Biomarkers (Plasma AVP Concentration, Plasma Renin Activity, Plasma BNP Concentration, Serum NT-proBNP Concentration, and Serum Troponin I Concentration)

At the specified time points, venous blood will be collected for the following examinations and tests, and the date and time of blood sampling will be recorded in the source document and the eCRF.

- Serum sodium concentration
- Serum potassium concentration
- Serum osmolality
- Biomarkers (plasma AVP concentration, plasma renin activity, plasma BNP concentration, serum NT-proBNP concentration, and serum troponin I concentration)

For the procedures for sample collection, processing, and storage, see [Appendix 1](#).

All the samples will be shipped to the central laboratory. The central laboratory will centrally measure the laboratory parameters according to the procedures specified by the laboratory and report the results of the measurements to the sponsor and the investigator or subinvestigator. An electronic file containing the measurement results will be provided to the sponsor from the central laboratory; therefore, entry in the eCRF will be unnecessary.

In addition to the serum sodium and potassium measurement at central laboratory, serum sodium and potassium concentrations will also be measured at the trial site for appropriate fluid management during the screening and treatment periods and the results of the local measurements will be recorded in the source document. The result of the serum sodium concentration measurement will also be recorded in the eCRF. If serum sodium and potassium concentration measurement is difficult to perform at the trial site, plasma sodium and potassium concentrations may be measured. Either serum or plasma

samples should be used consistently for measurement of sodium and potassium concentrations in a given subject. However, serum sodium and potassium concentrations will be measured in the central laboratory.

Serum sodium and potassium concentrations for pharmacodynamic assessment will be replaced by the data obtained as part of the clinical laboratory tests performed at the same blood sampling point as specified in [Section 3.7.2.2](#).

3.7.5.1.5 Urine Sodium Excretion, Urine Potassium Excretion, and Urine Osmolality

1) Measurements at the central laboratory

From the urine collected for each interval shown in [Table 3.7.5.1.1-1](#), a sample will be taken. For the procedures for sample collection, processing, and storage, see [Appendix 1](#).

All the samples will be shipped to the central laboratory. The central laboratory will centrally measure the laboratory parameters according to the procedures specified by the laboratory and report the results of the measurements to the sponsor and the investigator or subinvestigator. The original document for the measurement results is an electronic file provided to the sponsor from the central laboratory; therefore, entry of the measurement results in the eCRF will be unnecessary.

If urine collection for measuring daily urine volume cannot be made because part of the urine is discarded or for other reasons, no sample will be shipped to the central laboratory. The urine sodium concentration, urine potassium concentration, and urine osmolality on that day will be handled as missing data.

2) Urine sodium excretion and urine potassium excretion

Urine sodium excretion and urine potassium excretion will be calculated by multiplying the urine sodium concentration and the urine potassium concentration obtained at the central laboratory, respectively, by the urine volume.

Urine sodium and potassium excretions will be calculated by the sponsor; therefore, entry in the eCRF will be unnecessary.

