	6 to 8 hours after start of IMP administration	+4 hours ^a
	8 hours after start of IMP administration to immediately before start of IMP administration on the next day	
Urine sampling for the measurement of urine sodium concentration, urine potassium concentration, and urine osmolality	At the end of each urine collection interval shown in Table 3.7.1.2-1	
12-Lead ECG	1 hour after start of IMP administration	+1 hour
Vital signs (blood pressure, pulse rate, and body temperature)	1 hour after start of IMP administration	+1 hour
	4 hours after start of IMP administration	+1 hour
	8 hours after start of IMP administration	+4 hours
Serum osmolality, serum sodium concentration, and serum potassium concentration (Serum sodium and potassium concentrations will be measured also at the trial site.)	4 hours after start of IMP administration	+1 hour
	8 hours after start of IMP administration	+4 hours

^aAllowable time window for the end of each interval

6) At a feasible time after start of IMP administration

- Dyspnea (respiratory rate, paroxysmal nocturnal dyspnea, orthopnea, and subject-assessed dyspnea)
- Congestive symptoms (lower limb edema, hepatomegaly, jugular venous distension, pulmonary rales, and cardiac third sound)
- Physical examination
- Adverse Events
- Concomitant medications and therapies
- Confirmation of IMP compliance

7) Adjustment of infusion solution

Infusion solution will be checked and adjusted at least 3 times to correct electrolyte abnormalities based on the blood pressure, pulse rate, body weight, serum sodium

concentration, serum potassium concentration, urine volume, fluid intake, and other parameters measured before, and at 4 and 8 hours after start of IMP administration.

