3.7.1.5 Dose Escalation Day (Day 2 or Day 3)

On the day on which the dose is increased (the first day OPC-61815 is administered at 16 mg), the following examinations and tests will be conducted.

1) Urine Collection

Urine will be collected at the intervals shown in [Table 3.7.1.5-1](#). At the end of each interval, subject are required to urinate completely to start urine collection for the next interval.

Table 3.7.1.5-1 Urine Collection Intervals on the Dose Escalation Day	
Urine collection interval	Allowable time window for the interval end
0 to 4 hours after start of IMP administration	+1 hour
4 to 8 hours after start of IMP administration	+4 hours
8 hours after start of IMP administration to immediately before IMP administration on the next day	

2) Examinations and tests after start of IMP administration

In addition to the procedures scheduled for each day, the examinations and tests shown in [Table 3.7.1.5-2](#) will be conducted at each time point.

Table 3.7.1.5-2 Examinations/Tests and Timing on the Dose Escalation Day

Item	Timing	Allowable time window
Urine volume and fluid intake	0 to 4 hours after start of IMP administration	+1 hour ^a
	4 to 8 hours after start of IMP administration	+4 hours ^a
	8 hours after start of IMP administration to immediately before start of IMP administration on the next day	
Urine sampling for the measurement of urine sodium concentration, urine potassium concentration, and urine osmolality	At the end of each urine collection interval shown in Table 3.7.1.5-1	
Vital signs (blood pressure, pulse rate, and body temperature)	4 hours after start of IMP administration	+1 hour
	8 hours after start of IMP administration	+4 hours
Serum osmolality, serum sodium concentration, and serum potassium concentration (Serum sodium and potassium concentrations will also be measured at the trial site.)	4 hours after start of IMP administration	+1 hour
	8 hours after start of IMP administration	+4 hours

^aAllowable time window for the end of each interval

3) Adjustment of infusion solution

The following procedure will be added to the procedures scheduled for each day.

Infusion solution will be checked or adjusted at least twice after start of IMP administration to correct electrolyte abnormalities based on the blood pressure, pulse rate, body weight, serum sodium concentration, serum potassium concentration, urine volume, fluid intake, and other parameters measured at 4 and 8 hours after start of IMP administration.

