Dose escalation day	Point in time at which urination immediately before IMP administration is completed to 4 hour after start of IMP administration ^a	+1 hour
	4 to 8 hours after start of IMP administration ^a	4 hours
	8 hours after start of IMP administration to immediately before IMP administration on the next day ^a	
Day 2 and onward (except the dose escalation day)	Same as the urine collection interval (daily urine volume)	

^aUrine volume will be measured after urination at the end of the urine collection period is completed.

If the exact urine volume cannot be measured because part of the urine is discarded or for other reasons, the urine volume for that interval will be handled as missing data. If a diaper or an incontinence pad is used by necessity, urine volume may be estimated by comparing the weight of the diaper or incontinence pad before and after use (converting 1 gram to 1 milliliter).

The daily urine volume on Day 1 or the dose escalation day will be the sum of the urine volumes for all the measurement intervals on that day (the daily urine volume will be calculated by the sponsor; therefore, entry in the eCRF will be unnecessary).

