### **11.4 Urine Sodium Excretion, Urine Potassium Excretion, Urine Osmolality**

Descriptive statistics for measured values and changes from baseline at each time point will be calculated for daily urine sodium excretion and daily urine potassium excretion (0 to 24 hours).

Descriptive statistics for measured values at each time point will be calculated for interval urine sodium excretion and interval urine potassium excretion (0 to 4 hours, 4 to 8 hours, and 8 to 24 hours) on Day 1 and the day of dose escalation (Day 2 or Day 3).

Descriptive statistics for measured values at each time point will be calculated for cumulative urine sodium excretion and cumulative urine potassium excretion (0 to 4 hours, 0 to 8 hours, and 0 to 24 hours) on Day 1 and the day of dose escalation (Day 2 or Day 3).

Descriptive statistics for measured values and changes from baseline at each time point will be calculated for urine osmolality.

Note that urine sodium excretion and urine potassium excretion will be calculated by multiplying the urine sodium concentration and the urine potassium concentration obtained at the central laboratory, respectively, by urine volume.

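### Read literally, the day-level missing-data rule for urine chemistry can discard intact interval samples on Day 1 and the dose escalation day (minor; descriptive pharmacodynamic tables only)

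*Protocol*

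**What the plan says.** **Sampling is by interval.** Protocol 3.7.5.1.5 says where its sample comes from: "From the urine collected for each interval shown in", with reference to Table 3.7.5.1.1-1. That table divides Day 1 and the dose escalation day into three collection intervals: 0–4 h, 4–8 h, and 8 h to the next predose. Protocol 3.7.1.2 times the Day 1 samples "At the end of each urine collection interval shown in Table 3.7.1.2-1", and Protocol 3.7.1.5 times those of the escalation day "At the end of each urine collection interval shown in Table 3.7.1.5-1". Day -1 and the other treatment days have one collection of about 24 h.

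**The missing-data rule for chemistry is by day.** Protocol 3.7.5.1.5 sets the condition: "If urine collection for measuring daily urine volume cannot be made because part of the urine is discarded or for other reasons, no sample will". The sentence ends by ruling out shipment of a sample. For the results, the section then states: "The urine sodium concentration, urine potassium concentration, and urine osmolality on that day will be handled as missing data".

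**The missing-data rule for volume is by interval.** Under Protocol 3.7.5.1.1, when an exact volume cannot be obtained, "the urine volume for that interval will be handled as missing data". Weighing a diaper or pad is allowed as an estimate of volume. The section also says: "The daily urine volume on Day 1 or the dose escalation day will be the sum of the urine volumes for all the measurement intervals".

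**The analysis is by interval.** SAP 11.4 tabulates "interval urine sodium excretion and interval urine potassium excretion (0 to 4 hours, 4 to 8 hours, and 8 to 24 hours". These tables cover both Day 1 and the escalation day, and cumulative excretion is planned over 0–4 h, 0–8 h and 0–24 h. SAP 3.4 explains how interval values are added up to a daily value. SAP 5.4 covers only missing data at the final administration time point. Neither gives an interval-level rule for urine chemistry.

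**The concern.** Sampling, the volume rule and the planned tables all work by interval, while the chemistry rule works by day. Excretion is concentration times volume. Suppose urine is lost only overnight on Day 1. The 0–4 h and 4–8 h volumes remain valid, and those samples were taken from complete collections. Under the literal rule their concentrations and osmolality are nevertheless missing, so the excretions for those intervals cannot be calculated.

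At stake are the urine sodium, potassium and osmolality summaries for the first 8 mg day and the first 16 mg day, which Protocol 3.5.2 lists among the measures of the aquaretic effect. Volume and excretion tables for the same interval could also rest on different subjects for no analytical reason. Sites could differ too: one that ships each sample at once would produce results that another, holding samples until the day ends, would not.

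**Working it through.** **Plan figures.** The documents give no rate of urine loss, so there is no planned figure to reproduce on this point. The only design figure is the chance of seeing at least one adverse event in 40 subjects. It checks (1 − 0.95^40 = 87.1% and 1 − 0.96^40 = 80.5%, against 87% and 80% stated) but has no bearing here.

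**Does one lost interval trigger the day rule?** On Day 1 and the escalation day the daily volume is a sum over all measurement intervals. If one is missing, the sum is incomplete. Protocol 3.7.5.1.5 does not exempt these days, so on its words the rule applies and all three samples become missing instead of one.

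**Collection and measurement intervals differ on Day 1.** There are three collection intervals but six volume measurement intervals: 0–1, 1–2 and 2–4 h (within 0–4 h), 4–6 and 6–8 h (within 4–8 h), and 8 h to the next predose. On the escalation day the two sets coincide. An interval rule for excretion has to allow for this nesting.

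**Illustration for Day 1.** Assumptions: all 40 subjects contribute to Day 1; each collection interval is lost with probability q, independently; three intervals per day. The values of q are not taken from the documents.

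- Interval rule: share lost from an interval = q; usable samples = 40(1 − q).
- Day rule: share lost from every interval = 1 − (1 − q)^3; usable samples = 40(1 − q)^3.
- Intact samples discarded, out of 3 × 40 = 120: 120[(1 − q) − (1 − q)^3].

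| q | Lost, interval rule | Lost, day rule | Usable 0–4 h, interval rule | Usable 0–4 h, day rule | Intact samples discarded of 120 |
|---|---|---|---|---|---|
| 2% | 2% | 5.9% | 39.2 | 37.6 | 4.7 |
| 5% | 5% | 14.3% | 38.0 | 34.3 | 11.1 |
| 10% | 10% | 27.1% | 36.0 | 29.2 | 20.5 |
| 20% | 20% | 48.8% | 32.0 | 20.5 | 34.6 |

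For cumulative 0–8 h excretion the interval rule needs two complete intervals, 40(1 − q)^2, so the gap is smaller: 36.1 against 34.3 at 5%, 32.4 against 29.2 at 10%, and 25.6 against 20.5 at 20%. For 0–24 h excretion the two rules give the same result, because all three intervals are needed.

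**Dependence.** If losses cluster within subjects, the gap narrows. In the extreme where a subject loses either all three intervals or none, both rules drop the same share q and there is no gap.

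**The case against.** The strongest reply is that the rule was written for single-collection days. Its trigger is that the collection for daily urine volume cannot be made. Elsewhere that term, as something collected or measured, belongs to the 24 h collections: Table 3.7.5.1.1-2 attaches it only to Day -1 and to Day 2 onward except the escalation day, and note b of Table 3.7-1 uses it in the same way. On Day 1 and the escalation day the daily volume is a total calculated by the sponsor. On a single-collection day one lost void spoils the only sample, so nothing intact is thrown away. This reading is plausible. It does not remove the point, because the section opens by covering every interval in Table 3.7.5.1.1-1 and does not then narrow the rule. If the narrow reading was intended, the same clarification is needed.

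Other parts of the reply stand and limit the point:

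- A reader might infer that any lost urine blanks the day. The trigger is failure of the daily collection, and a weighed diaper or pad can still supply a volume.
- A reader might infer that incontinent or sicker subjects would be selectively lost. The documents give nothing to show this, and the pad provision works against it for volume. Where a pad gives a volume but no urine to sample, volume and excretion tables will differ in their subjects even after the fix.
- A reader might infer that about 11 of 40 subjects would be lost on both days. That number comes from an assumed 10% and independence, and it can describe Day 1 only. The escalation day includes only subjects who were escalated, and SAP 14 says their distribution differed from what was expected.

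**Conclusion.** The inconsistency is real on the text: a day-level rule for chemistry stands beside an interval-level rule for volume and interval-level tables in the SAP, and nothing in the SAP resolves it. The documents do not show that valid data have been or will be deleted, only that the literal wording permits it on days with several collection intervals.

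The size is unknown. Under the assumptions above, 5% to 20% loss per collection interval becomes about 14% to 49% loss from each Day 1 interval, and less if losses cluster.

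The priority is minor. No primary or secondary outcome variable is set (SAP 6.1, 6.2), and the affected outputs are descriptive. A reader might suppose that the tolerability conclusion or the dose escalation decision is touched. Neither is: the escalation criteria in Protocol 3.2.2 use urine volume, body weight, congestive symptoms, serum or plasma sodium and investigator judgment, and the sodium event counts in SAP 9.3 use serum values.

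**What to change.** Amend Protocol 3.7.5.1.5, and mirror the text in SAP 11.4, to state:

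- On days with several collection intervals, only the affected collection interval (0–4 h, 4–8 h, or 8 h to next predose) is missing for concentration, osmolality and excretion. Samples from complete intervals are shipped and analysed.
- A collection interval's excretion is missing if any volume measurement interval within it is missing; on Day 1, for example, 1–2 h within 0–4 h.
- Daily totals, and cumulative totals that span a lost interval, are missing.
- The whole-day rule stays for days with a single 24 h collection.

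The cost is a few sentences in each document. The samples are already taken under the plan, so no procedure is added. Samples that were never shipped may not be recoverable, but results already held by the central laboratory can be kept.

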3.7.5.2 Pharmacogenomic Assessment

3.7.5.2.1 DNA Storage

1) Rationale for DNA Storage

In this trial, DNA samples will be stored on a voluntary basis. DNA storage will be conducted on subjects who provide written consent, only at trial sites that provide prior agreement regarding DNA storage.

In Q&A 1 in the “Clinical Trials using Pharmacogenomics” (PFSB/ELD Notification No. 0930007 of the Evaluation and Licensing Division, Pharmaceutical and Food Safety Bureau, Ministry of Health, Labour and Welfare [MHLW] dated 30 Sep 2008)¹⁰, the MHLW states that DNA samples for possible genomic/genetic analysis to evaluate the IMP (PK, efficacy, safety, etc.) may be collected from subjects during the clinical trial in either of the following cases: 1) the target and timing of the potential genomic/genetic analysis has been specifically identified at the time of the trial, or 2) although the target or timing of the potential genomic/genetic analysis has not been specifically identified at the time of the trial, but it is planned to conduct analysis for the evaluation of the IMP in future. The MHLW also states in Q&A 2 in the same notification, that samples for possible genomic/genetic analysis with a purpose independent of the evaluation of the IMP may be collected from subjects during the trial. Furthermore, Section 1.4 General Principles of The International Council for Harmonization (ICH) E18 Guidelines, “Genomic Sampling and Management of Genomic Data” states that, “With advances in science and increased awareness of the impact of genomics, there is a need and an opportunity to maximize the value of collected samples and the data generated therefrom. Therefore, genomic sample acquisition is strongly recommended in all phases and studies of clinical development.”¹¹

In this trial, the collection of DNA samples is planned to coincide with other trial examinations and tests to minimize the burden on the subjects. Thus, the voluntary collection and storage of DNA samples in this trial is appropriate.

2) Purposes

Samples for DNA analysis will be collected from the subjects to enable a future exploratory investigation regarding DNA variants relating to individual differences in responsiveness (eg, efficacy, safety, PK) to the IMP, and/or the disease-associated DNA variants.

3) Target subject group

DNA storage will be conducted at trial sites at which the IRB provides prior approval for blood sampling for DNA storage. A blood sample for DNA storage will be collected only from subjects who provide voluntary consent to DNA storage.

4) Timing of blood sampling

A blood sample for DNA storage will be collected at predose on Day 1. If a blood sample cannot be collected at predose on Day 1 or re-collection is required for any reason, blood sampling may be repeated at a feasible time during the trial period. The date and time of blood sampling will be recorded in the source document and the eCRF.

5) Sample for DNA storage

For the detailed procedures for sample collection, handling, and shipment, see [Appendix 1](#). The DNA samples will be stored until 1) possible genomic/genetic analysis is determined to be unnecessary, 2) 15 years has passed since informed consent has been obtained from the first subject, or 3) the subject withdraws consent to DNA storage, whichever comes first.

3.7.5.2.2 Potential Genomic/Genetic Analysis

Genomic/genetic analysis will be conducted if analysis is determined to be useful for the purposes described in [Section 3.7.5.2.1 2](#)).

When it is determined to conduct genomic/genetic analysis, a pharmacogenomics protocol will be prepared and approved by the research review committee at the sponsor, and the analysis will be then conducted according to applicable regulations. The results of the genomic/genetic analysis will not be included in the final study report, but documented separately as a research report.

The target of potential genomic/genetic analysis has not yet been identified. Genome-wide association analysis using DNA chips, DNA microarrays, or next-generation DNA sequencers may be conducted, however, the results of the analysis will not be used for purposes other than those described in [Section 3.7.5.2.1 2](#)).

DNA samples for possible genomic/genetic analysis will be double coded by the DNA repository and shipped to the genomic/genetic analysis laboratory (not yet designated), at which the genomic/genetic analysis will be conducted using the double-coded samples.

1) Informed consent for participation in DNA storage and its withdrawal

Written information regarding DNA storage and possible genomic/genetic analysis using DNA samples will be prepared separately from written information for the trial,

and informed consent for participation in DNA storage will be obtained from the subject. The date of the informed consent obtained from the subject will be recorded in the source document and the eCRF. Consent from subjects who are able to consent, but unable to sign the ICF for physical or therapeutic reasons will be obtained in a manner similar to that described in [Section 3.4.1](#).

If a subject withdraws the consent for DNA storage during the storage period, the sponsor will request the biorepository to discard the sample of the subject, and the biorepository will discard the samples in such a way that the subject cannot be identified. If individual samples cannot be identified because information connecting samples and subjects identifiers (eg, code list) is destroyed or for other reasons, the sample of a subject who withdraws consent may not be consequently discarded.

Withdrawal from participation in the trial will not result in withdrawal from participation in DNA storage. If the results of a potential genomic/genetic analysis have been obtained at the time of consent withdrawal, the results will not be discarded.

2) Disclosure of the results of genomic/genetic analysis to subjects

Even if some information is obtained from the genomic/genetic analysis, the analysis results will be only exploratory and at an early stage of research, and their scientific reliability such as precision or certainty will not have been adequately demonstrated. Disclosure of information without established scientific reliability will not be beneficial to subjects. Therefore, the sponsor will not disclose the results of genomic/genetic analysis to subjects, in principle.

